3.1 Study Visits

Visit 1: subjects will come to the UAMS IOA 3rd floor for informed consent discussion. Once consent is obtained, subsequent study procedures will be performed. A medical history including allergies and list of current medications will be obtained (printed from Epic if they are a UAMS patient). Subject height, weight, and vital signs will be measured. A blood sample will be drawn for complete blood count [CBC]. A physical exam will be performed at this visit or at visit 2 or 3 at the discretion of the study physician. A DEXA scan for whole-body analysis will be performed in the PI's lab at UAMS (or at visit 2). Subjects can get a copy of their CBC and DEXA scan upon request. Any abnormal findings will be discussed with them by the study nurse and/or physician. Based upon the results of the screening blood sample, visit 2 will be scheduled.

Visit 2: Subjects return to the UAMS IOA. They will be asked about any adverse events since last visit. If not performed at visit 1, the physical exam and/or DEXA scan will be performed at this visit. Randomization will be performed as mentioned below. Subjects will be provided with complete, ready-to-eat meals that they will consume for 3 consecutive days prior to their stable isotope study visit (visit 3). They will be loaned a digital camera to document their compliance for these meals. Visit 3 will be scheduled. See Appendices for menus of the 3 days of meals. Food volume will be tailored for age/sex/body weight so that subjects do not gain or lose weight during the diet run-in period. A UAMS dietician will prepare the specific menus for each

subject, and UAMS Clinical Nutrition staff will prepare and package the meals in the IOA research kitchen located on the 3rd floor of the IOA.

Visit 3: Subjects will return to the IOA having fasted overnight from 10:00 P.M. They will also return their loaner camera. They will be asked about any adverse events since last visit. Study staff will ascertain that subjects complied with the meal requirements prior to proceeding with the stable isotope infusion study. If not performed earlier, the physical exam will be done at this visit.

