3.4 Randomization

We will use permuted block randomization, with random block sizes of 2 or 4, to assign subjects to one of three possible treatment groups. The permuted block design will ensure that group sizes are equal after each block is filled. In addition, the randomization procedure will be stratified by gender to guard against group imbalance. A randomization procedure will be implemented using sealed envelopes, each one being labeled with stratification level (gender) and a label number. The label numbers will be sequential within each of the groups. As a participant is identified and enrolled on study, the study coordinator will ascertain gender, which will determine the set of randomization envelopes to be used. The study coordinator will choose the lowest numbered envelope, which will reveal group assignment. In the event of incomplete subjects that significantly unbalance the groups, subsequent subjects will be randomized into remaining unfilled groups.

A: subjects will consume 2 ounces of cooked pork loin one time during the stable isotope study visit.

B: subjects will consume 1 ounce of mixed nuts one time during the stable isotope study visit.

C: subjects will consume 4 ounces of tofu one time during the stable isotope study visit.

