3.5 Blinding

This is a single-blinded study. The PI and any other data analysts are blinded to test meal. After all study visits have been performed and all data entered into a database, the blind will be broken.

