4.2 Exclusion Criteria

- History of diabetes
- History of malignancy in the 6 months prior to enrollment
- History of gastrointestinal bypass/reduction surgery (Lapband, gastric sleeve, etc.)
- History of chronic inflammatory condition or disease (Lupus, HIV/AIDS, etc.)
- Pregnant females
- Subjects who do not or will not eat animal proteins
- Subjects allergic to pork, tree or peanuts, or soybeans
- Subjects who cannot refrain from consuming protein or amino acid supplements during their participation in this study

- Subjects who report regular resistance training exercise > once per week
- Hemoglobin <9.5 g/dL at the screening visit
- Platelets < 150,000 at the screening visit
- Concomitant use of corticosteroids (ingestion, injection or transdermal)
- Any other disease or condition that would place the subject at increased risk of harm if they were to participate, at the discretion of the study physician

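### Random blocks of 2 or 4 cannot split three groups equally, so the balance promised in section 3.4 is not delivered; the refill sentence is a smaller, separate gap

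*Combined protocol and SAP*

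**What the plan says.** Section 3.4 describes permuted blocks "with random block sizes of 2 or 4, to assign subjects to one of three possible treatment groups", stratified by gender, and then states: "The permuted block design will ensure that group sizes are equal after each block is filled". The groups are pork, mixed nuts and tofu. Assignments sit in sealed, sequentially numbered envelopes, one set per gender: "The study coordinator will choose the lowest numbered envelope, which will reveal group assignment".

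The same section ends its procedure with a refill rule: "In the event of incomplete subjects that significantly unbalance the groups, subsequent subjects will be randomized into remaining unfilled groups". Nothing in the document puts a number on the imbalance that triggers it, says who decides, says where the redirected assignments come from or how they are concealed, or says whether the gender strata still apply.

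Section 3.5 calls the study single-blinded: "The PI and any other data analysts are blinded to test meal". The coordinator is not on that list. Section 7.2 sets 24 subjects, 8 per protein source. Section 4.0 allows up to 30 to be enrolled. Section 3.2 drops subjects who eat too little of the run-in meals or do not finish the test meal. Both events follow randomisation at visit 2, so incomplete subjects are foreseeable. No drop-out rate is given.

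**The concern.** The block sizes and the equality statement contradict each other. Whoever prepares the envelopes cannot build the list as described and has to improvise how a block of 2 or 4 is shared among three groups. The stated purpose of blocking, and the 8 per source behind the power calculation, are then met only by luck.

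The second and smaller issue is the refill rule. It concerns only imbalance caused by incomplete subjects. Once it is in force and a single group remains open, the next assignment is not random at all, and the person who opens the envelopes can know it beforehand. At stake is allocation concealment for a few late subjects.

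**Working it through.** **1. The plan's own power figure.** Inputs from sections 7.1 and 7.2: N = 24, three groups, one covariate explaining R² = 0.5, α = 5%, f = 0.484.

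- Degrees of freedom: 3 − 1 = 2 and 24 − 3 − 1 = 20.
- Noncentrality: λ = N f²/(1 − R²) = 24 × 0.2343/0.5 = 11.24.
- Power from the noncentral F distribution: 80.0%. The plan's figure reproduces, as do all five rows of its Table 1.

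**2. Divisibility.** 2 = 0 × 3 + 2 and 4 = 1 × 3 + 1. A block of 2 omits at least one group. A block of 4 is at best 2:1:1. Equality within a block is impossible, and equality of running totals is accidental.

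**3. Size of the imbalance.** The document does not say how such blocks would be filled. Assumed: a block of 2 holds two different groups chosen at random; a block of 4 holds each group once plus one more at random; both sizes are equally likely; gender is 50/50 at random; 24 subjects, no drop-out. Simulation of 20,000 trials (40,000 for the 8/8/8 row):

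| Result at 24 subjects | Blocks of 2 or 4 | Blocks of 3 or 6 |
|---|---|---|
| Largest minus smallest group is 3 or more | 53% | 4% |
| Smallest group is 6 or fewer | 42% | 2% |
| Exactly 8/8/8 | 9% | 41% |
| Mean power | 79.0% | 79.8% |

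Within a stratum of up to 12 subjects, only about 8% of filled blocks of 2 or 4 leave the three running totals equal. With blocks of 3 or 6 all of them do. The 41% falls short of 100% because the last block in each gender stratum is usually unfinished.

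**4. Power in one unbalanced trial.** Take pork above two equal groups by d standard deviations. Then f² = 2d²/9, so d² = 4.5 × 0.2343 = 1.054. With n in pork, λ = [n(N − n)/N] × d²/(1 − R²).

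- 8/8/8: (8 × 16/24) × 1.054/0.5 = 11.24, power 80.0%.
- 6 in pork, 9 and 9: (6 × 18/24) × 1.054/0.5 = 9.49, power 72.6%.
- 10 in pork, 7 and 7: power 83.6%.

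Imbalance can therefore help or hurt under this pattern, which is why the mean barely moves.

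**5. The refill rule.** With one group open, the next assignment is certain. With two equally open groups the best guess is right half the time. With three equally open it is right one time in three, and nothing is gained.

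How often the certain case arises cannot be derived from the document. Assume 10% or 20% drop-out, up to 30 randomised, redirection only from subject 25, each outcome known before the next assignment, and a trigger anywhere from redirecting everyone to requiring a gap of 3 completers. On lists in the protocol's own blocks of 2 or 4, at least one certain assignment then occurs in 43% to 72% of trials at 10% drop-out and 43% to 68% at 20% (12,000 trials per scenario). Few subjects are involved: if everyone after the 24th is redirected, 2.6 per trial at 10% and 4.9 at 20%, not all of them with one group open.

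For comparison, on an ordinary list with undisclosed blocks of 3 or 6 and no redirection, someone tracking the sequence is certain at least once after subject 24 in 19% and 34% of trials.

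**The case against.** The strongest reply is that little is lost. Subjects are still assigned at random from sealed envelopes, totals can still come out equal, and on the assumed filling mean power falls by 79.8 − 79.0 = 0.8 points. That stands, and it limits the weight of the point. It does not rescue the equality statement, which is false whatever filling is used.

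On the refill rule the reply is also fair. Few late subjects are affected, the PI and analysts are blinded, and an ordinary list is itself partly predictable near the end. The frequencies rest on drop-out rates and a trigger that the document does not give.

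Four stronger readings are tempting and not supported:

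- *The randomisation cannot work at all.* Only the promised equality fails. A list can still be made and used.
- *The block error makes refilling more frequent.* The sentence is triggered by incomplete subjects, not by imbalance from the blocks.
- *The coordinator can select subjects by arm.* Randomisation is at visit 2, and the physical exam may come as late as visit 3 ("If not performed earlier, the physical exam will be done at this visit"), so a discretionary exclusion could follow the reveal. But consent, history and blood count precede the envelope, that exclusion rests with the study physician, and nothing says the physician learns the arm or that the coordinator decides eligibility.
- *The figures of 24 studied and 30 enrolled conflict.* They can be read together as 24 completers plus room for replacements.

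**Conclusion.** The point holds, and the block sizes should be corrected. The contradiction between blocks of 2 or 4 and equal thirds is arithmetic and rests on no assumption; no other section corrects it. Its practical size does rest on an assumed way of filling the blocks: a gap of 3 or more in about half of trials instead of about 1 in 25, with under one point of mean power at stake and a larger loss only in an unlucky trial.

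The refill gap is real but secondary. The rule lacks a number, a decision-maker and a concealed source, and it makes an assignment certain whenever one group is open. The document supports saying that a few assignments can be known in advance. It does not support saying that they will be, or that the endpoint is biased.

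**What to change.** **Block sizes (wrong as written).** In section 3.4, replace the sizes with 3 or 6 within each gender stratum, do not disclose them to the coordinator, and limit the equality statement to filled blocks within a stratum. This costs one sentence and a new list.

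**Replacements (smaller).** Have each replacement take the next sealed envelope in the list for that subject's gender, with envelopes prepared up to the cap of 30, in place of the refill sentence. If redirection is kept, fix its numeric trigger in advance and have existing staff who do not enrol subjects draw the assignment from a concealed source. A fixed trigger alone does not remove certain assignments; concealment has to do that.

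**Cost.** Completer counts become slightly less equal. With blocks of 3 or 6 and 30 randomised:

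| Assumed drop-out | Power, no redirection | Power, all redirected after the 24th | Smallest group 6 or fewer (none / all redirected) |
|---|---|---|---|
| 10% | 79.5% | 79.9% | 17% / 1% |
| 20% | 77.3% | 77.8% | 42% / 20% |

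The power cost is about half a point when losses are even. If they concentrate in pork (assumed 30% against 5% and 5%) and pork alone differs, it is 73.4% without redirection against 78.1% with it. That is the main reason the trial team might keep a pre-set, concealed redirection rule.

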3.5 Blinding

This is a single-blinded study. The PI and any other data analysts are blinded to test meal. After all study visits have been performed and all data entered into a database, the blind will be broken.

3.6 Sample Storage

Blood and muscle samples will be kept frozen at -80 degrees Centigrade or colder once the initial processing has taken place. Samples shall be stored in appropriate freezers in the PI's laboratory, located in a restricted area inside the UAMS IOA building. Said freezers are monitored continuously for proper temperature and working condition. With explicit permission from subjects via the consent form, muscle samples will be kept indefinitely for approved use

in the PI's lab for metabolic or metabolomic analyses. Samples that have not been approved for future use by the subject will be destroyed only after all data has been analyzed and reported to the sponsors. All blood and muscle samples shall be identified using a unique study acronym. None of a subject's personal identifiers shall be present on any biological sample.

4.0 Study Population

Subjects will be recruited using these methods: 1) past subjects that indicated they wanted to be contacted about future studies will be called by study staff to elicit their interest in this study, 2) the study staff will place IRB-approved flyers around the Little Rock community, 3) study staff will engage Research Match.org, and 4) study staff will engage ARResearch program through the UAMS TRI. Once a potential subject has agreed to come to UAMS for an informed consent discussion, an appointment will be made for them to meet with study staff in the research area of the 3rd floor of the Reynolds Institute at UAMS. This study will enroll up to 30 subjects

4.1 Inclusion Criteria

- Ages 18-40 yrs.

4.2 Exclusion Criteria

- History of diabetes
- History of malignancy in the 6 months prior to enrollment
- History of gastrointestinal bypass/reduction surgery (Lapband, gastric sleeve, etc.)
- History of chronic inflammatory condition or disease (Lupus, HIV/AIDS, etc.)
- Pregnant females
- Subjects who do not or will not eat animal proteins
- Subjects allergic to pork, tree or peanuts, or soybeans
- Subjects who cannot refrain from consuming protein or amino acid supplements during their participation in this study

- Subjects who report regular resistance training exercise > once per week
- Hemoglobin <9.5 g/dL at the screening visit
- Platelets < 150,000 at the screening visit
- Concomitant use of corticosteroids (ingestion, injection or transdermal)
- Any other disease or condition that would place the subject at increased risk of harm if they were to participate, at the discretion of the study physician

5.0 Risks and Benefits

There are no direct benefits for the subjects. Expected risks associated with this protocol are described in detail below. All experimental procedures will be performed by appropriately trained and credentialed personnel.

5.1 Blood sampling:

Blood samples will be collected solely for the purpose of experimentation. The blood will be used to determine eligibility and to measure glucose, insulin, plasma amino acid concentrations and stable isotope concentrations. The total amount of blood taken will be approximately 96 mL. Subjects will have no noticeable effects.

5.2 DEXA scan:

The DEXA scan exposes subjects to approximately ½ of the radiation of one chest x-ray. They will undergo 1 DEXA scan.

5.3 Muscle samples:

Briefly, the risks related to the biopsy procedure include pain, bleeding, bruising, small scar formation at the biopsy site, infection, and vaso-vagal response. Muscle biopsies are performed by a physician utilizing local anesthesia (using 1% plain lidocaine) for pain management and strict sterile procedures. Subjects must meet platelet criteria prior to biopsy. See appendices for SOP and related documents.

5.4 Test meals:

Subjects who are allergic to one of the test meal components will not be permitted to participate. Their allergies will be ascertained during the initial phone call or at visit 1.

5.5 Confidentiality:

A potential risk to study participants is the potential for loss of confidentiality. Measures to protect the confidentiality of study participants will be implemented as described in the Data Handling and Recordkeeping section below.

5.6 Stable Isotope Infusion:

Briefly, the risk related to the isotope infusion is pyrogenic response. All isotope infusions are compounded and prepared by a licensed pharmacist at UAMS. An SOP for infusion procedures will be utilized (see Appendix). All stable isotopes are tested for sterility and pyrogenicity. The stable isotopes will be filtered during infusion through a sterile 0.22 micron (Millipore) filter placed in the infusion line. Stable isotopes are naturally occurring compounds and are not radioactive and are already present in the body in varying amounts. The infusion will be in a 'tracer' dose, i.e., a dose only detectable by GCMS. Infusion of these molecules will increase the level of naturally occurring isotopes by 7-10%. Any adverse reactions during the isotope infusion that suggest infection (urticaria, flushing, nausea, vomiting, sweating, chills, altered heart rate, hypo/hypertension, and hyperthermia) will be promptly addressed by the study physician. Depending on the seriousness of the reaction, the infusion study will be terminated.

6.0 Data Handling and Recordkeeping

Source documents and CRFs will be stored in a secure area of the PI's laboratory. Access will be limited to study personnel. Documents containing identifiers (except the signed ICF) will be destroyed by shredding approximately 7 years after data analysis is completed or publication of data; whichever is longest. The original, signed ICF will be kept indefinitely. At no time shall Protected Health Information be released to non-study personnel.

The Principal Investigator will carefully monitor study procedures to protect the safety of research subjects, the quality of the data and the integrity of the study. All study subject material will be assigned a unique identifying code or number. The key to the code (the instrument associating the data with subject identity) will be kept on a password-protected UAMS server, located behind locked doors in a restricted access area of the UAMS campus. Only those individuals listed on the title page of this protocol and their research staff members will have access to the code and information that identifies the subject in this study. This file will be deleted approximately 7 years after data analysis is completed.

7.2 Sample Size Calculation & Power Analysis

A total of N=24 subjects (8 per protein source) will be required for this study. With this sample size, the ANCOVA model will have 80% power to detect effect sizes of $f = 0.484$ or larger (Table 1). This estimate assumes the basal covariate explains 50% of the variation in the response and a 5% α -level is used to determine statistical

Table 1. Expected Effect Size by Covariate Variation

Variation Explained by Covariate (%)	Detectable Effect Size, f
10	0.649
30	0.573
50	0.484
70	0.375
90	0.216

significance. (Note that the effect size, f , is simply the ratio of the variation between the three group means and the between-subject variation). In the event the effect of the covariate is mis-

specified, the following table presents effect sizes that can be detected as the magnitude of variation explained by the covariate increases from 10% to 90%.

8.0 Ethical Considerations

This study will be conducted in accordance with all applicable government regulations and University of Arkansas for Medical Sciences research policies and procedures. This protocol and any amendments will be submitted and approved by the UAMS Institutional Review Board (IRB) to conduct the study.

The formal consent of each subject, using the IRB-approved consent form, will be obtained before that subject is submitted to any study procedure. All subjects for this study will be provided a consent form describing this study and providing sufficient information in language suitable for subjects to make an informed decision about their participation in this study. The person obtaining consent will thoroughly explain each element of the document and outline the risks and benefits, alternate treatment(s), and requirements of the study. The consent process will take place in a quiet and private room, and subjects may take as much time as needed to make a decision about their participation. Participation privacy will be maintained and questions regarding participation will be answered. No coercion or undue influence will be used in the consent process. This consent form must be signed by the subject and the individual obtaining the consent. A copy of the signed consent will be given to the participant, and the informed consent process will be documented in each subject's research record.

9.0 Dissemination of Data

Results of this study may be used for presentations, posters, or publications. The publications will not contain any identifiable information that could be linked to a participant.

11.0 Appendices

11.1 CTRLAL Muscle Biopsy SOP

Policy: The following information is written to serve as a resource and guideline for the percutaneous vastus lateralis muscle biopsy procedure. This SOP will ensure that the procedure is performed in a consistent manner that protects participant safety. This procedure can be performed concurrently with a fat biopsy, provided that the protocol calls for samples at the same time-point. In this case, the fat bx shall be performed first so that the muscle bx site does not bleed during the performance of the fat bx.

Purpose: The muscle biopsy procedure is conducted to obtain a sample (~100-150mg) of muscle tissue for metabolic (and possibly structural) analyses.

Responsibility and Accountability:

Principal Investigator: Will oversee, direct, and be responsible for assuring adherence to the entire procedure.

Study Physician: Responsible for overall medical supervision and performance of the procedure including handling of subject complaints or adverse events related to muscle biopsies.

Study/staff nurse: Will assist study physician with their performance of muscle biopsy procedure. Will educate subject about post-biopsy care per the written instructions.

Materials:

Equipment: sterile 5mm (or 6mm) Bergstrom biopsy cannula.

Supplies: 1 betadine 3-swab pack, commercial preps, or chlorhexidine solution
2 drape sheets
1 fenestrated drape sheet
1 laceration tray

- 1 lidocaine 1% w/o epinephrine (from Rx)
- 2pr sterile gloves
- 2 packs non-adhesive dressing sponges
- 1 Opti-lock IV extension tubing
- 1 sterile IV extension tubing ~24" long
- 1 #11 scalpel
- 1 Dermabond glue
- 2 clear Tegaderm-type dressing
- 1 50 or 60 mL syringe for suction
- 1 5mL syringe for rinsing muscle
- 1 18g needle for rinsing muscle
- 1 5mL sterile saline for rinsing muscle
- 2 6" ace bandage

Pre-Procedure:

1. Verify subject has already completed the consent and screening process.
2. Nurse verifies that subject has not taken any blood-thinning medications recently.
 - a. Prohibited medication classes: antiplatelet agents, anticoagulant agents. If subject uses these medications as prescribed by their physician, they will not be allowed to undergo a muscle biopsy.
 - b. Aspirin or aspirin-containing compounds: subjects should wait 7 days after the last dose of aspirin was ingested before they undergo a muscle biopsy.
3. Staff will set up a sterile field containing the above supplies and bx needle.
4. Explain the procedure to subject in terms that they understand, including expected sensations and side effects.

Procedure:

1. The biopsy site (lateral thigh, 1/2 way between hip and knee) will be prepped with one of the prep solutions to ensure disinfection.
2. Physician performing the bx and nurse will properly don sterile gloves.
3. The prepped area will be draped using the supplied sterile materials.

4. Sufficient 1% lidocaine solution will be used to anesthetize the skin, subcutaneous tissue and fascia at the biopsy site using supplied syringe and needles. Limit lidocaine volume to less than 20mL per biopsy. Wait approximately 6-10 minutes after the initial injection before testing area for sensation.
5. Using aseptic technique and sterile scalpel, a small incision (approximately ¼ inch) will be made in the skin after adequate anesthesia has been confirmed.
6. The Bergstrom needle will be inserted through the incision site approximately ¾ to 1" past the fascia, and a muscle biopsy will be taken with the aid of suction.
7. After the bx needle has been removed, a person wearing sterile gloves will apply firm compression for at least 7 minutes to the biopsy site.
8. Muscle sample will be handed to study staff for appropriate processing.
9. After hemostasis has been achieved, the biopsy site will be cleaned, and if this is the only or final biopsy to be performed, a medical adhesive will be used to close the incision. A pressure dressing will then be applied, and the subject will be advised to keep the pressure dressing on for approximately two hours.
10. The subject will be provided written wound care instructions, and these will be reviewed verbally as well.

Post Procedure and Discharge:

1. Provide subject with written wound care instructions and ensure they understand the instructions.
2. Call subject within 72 hours after the most recent bx to follow up for any problems or concerns.

Emergency Procedures and Adverse Event Reporting:

If bleeding persists, apply additional pressure to the site where muscle was biopsied. If necessary, apply ice pack to area to assist with hemostasis. Refer to study protocol for reporting procedures.

Documentation:

The study staff will complete the Muscle Biopsy Procedure note for each bx performed. Notes will be filed in the CRF.

